## 3. STUDY OBJECTIVES

### 3.1. PRIMARY OBJECTIVES:

- 1) Provide feasibility data on the testing of umbilical cord blood for NfL and tau

## 4. STUDY DESIGN

### 4.1. DESIGN

### 4.2. EXPECTED PARTICIPANT NUMBERS

110 participants at Royal Prince Alfred Hospital

### 4.3. DURATION OF THE STUDY

6 months

### 4.4. ENDPOINTS

#### PRIMARY ENDPOINTS

95% confidence interval for mean umbilical cord plasma NfL of 3pg/mL or less

#### SECONDARY ENDPOINTS

Range of umbilical cord plasma NfL and tau values in healthy deliveries  
Correlation of umbilical cord plasma NfL and tau with adverse perinatal outcomes  
Correlation of umbilical cord plasma NfL and tau with intrapartum investigation results (e.g., CTG, scalp lactate)  
Correlation of umbilical cord plasma NfL and tau with intrauterine developmental abnormalities  
Influence of gestational age, mode of delivery, and birth weight on umbilical cord plasma NfL and tau

Influence of duration of 2 nd stage of labour on umbilical cord plasma NfL and tau Number of consented patients in whom an adequate sample for analysis is not collected
--

#### 4.5. CENTRE

Royal Prince Alfred Hospital

### 5. STUDY PARTICIPANTS

#### 5.1. INCLUSION CRITERIA

**Inclusion Criteria:**

Planned delivery at RPAH

Any route of delivery (vaginal delivery or elective/emergency caesarean sections)

Willingness to provide informed consent

English speaking to permit informed consent

#### 5.2. EXCLUSION CRITERIA

**Exclusion Criteria:**

Expected infeasibility of sample collection (at midwife's discretion)

[figure not shown]
Non-English speaking

Participants with a history of a psychological illness or other conditions which may interfere with their ability to understand the study requirements or provide consent

## 6. STUDY PROCEDURES

### 6.1. STUDY FLOW CHART

We will prospectively collect umbilical 3ml of cord blood from 110 placentae. Umbilical cord blood samples will be collected by midwives in theatre or the birthing suite. All patients giving birth will be eligible for inclusion in the study. The exclusion of specific patients (e.g., category 1 emergency caesarean cases) may be at the discretion of the midwife, if collection of umbilical cord blood samples is not feasible. Cord blood required for standard of care testing of rhesus and blood gas analysis will be taken as a priority. Only once the required sample volume for this purpose has been obtained will the additional blood for this study be collected. Cases where the patient was consented but an adequate sample of blood was not able to be taken, for whatever reason, will be recorded. Blood will be stored by the midwives in the fridge in a labelled box, for later collection by a member of the Department of Anaesthetics. Biospecimens will be sent to an external lab for analysis (see section 6.1.1).

We will access the medical records for all included patients. Data extraction will include: weight at birth, gestational age, duration of second stage of labour, mode of delivery, maternal and baby health history, antenatal care history, peripartum events and monitoring, and neonatal outcomes (see the Case Record form in the appendix).

#### 6.1.1 BIOSPECIMEN EXPORTATION AND ANALYSIS

Each sample will be spun and plasma aliquots will be stored in the department's freezer. All cyrovials are de-identified and barcoded, a bio-specimen log is kept on the secure server on the lab computer, only authorised research staff will have access to this log. De-identified plasma samples will be sent to [name], University of Gothenberg, Sweden for analysis. Samples will be sent via TNT or Auspost and will adhere to the company guidelines for biological samples sent by air. Additionally we will ensure to follow the National Pathology Accreditation Advisory Council document- requirement for packages and transport of pathology specimens and associated materials. We will use the services of a company to provide cold chain packaging materials (CoolPac), to comply with the requirements for safe export of biological materials and dry ice. The required forms -UN 3373 and UN1845 - will be completed prior to exportation of biological goods.

The laboratory in Sweden is highly secure with restricted access to University employees only. Only University personnel performing analysis will have access to the de-identified plasma samples and to the de-identified data. University laboratory staff will analyse the samples using SIMOA analysis of NfL and total tau. Additionally samples will be analysed for additional markers of injury (e.g. Glial Fibrillary Acidic Protein) and inflammation including cytokines (e.g. IL-6 and IL-8). The samples will be placed in hazardous waste and be destroyed by incineration after analysis.

A Material Transfer Agreement (MTA) will be submitted as part of the RPAH Governance requirements.

## 6.2. INVESTIGATION PLAN

### 6.2.1. METHODOLOGY

Interventions	Enrolment	Immediately post-delivery	2–4 weeks post-delivery
Participant Consent	✓		
Inclusion / Exclusion criteria	✓		
Adverse Event & Serious Adverse Event Assessment		✓	
Umbilical artery + vein blood sample collection		✓	
Patient medical record assessment			✓

### 6.2.2 ADVERSE EVENTS/SERIOUS ADVERSE EVENTS

We anticipate no serious or non-serious adverse events with our study.

## 6.3. STUDY PROCEDURE RISKS

There is a risk of blood exposure to the midwife collecting umbilical cord blood samples. This will be minimised by standard blood precautions including the use of personal protective equipment. There is a possibility of damage to placenta in the process of collecting umbilical cord blood samples, which may interfere with placental histopathology, if it is indicated. The overall risk of this is very low. Both of the aforementioned risks of our study are offset by the fact that cord blood sampling is taken as standard of care in all patients giving birth at RPA—we will only be adding to the amount of blood taken, rather than affecting the decision of whether blood should be taken or not. The extra 3mL of blood obtained as part of this study is unlikely to represent any meaningful increase in the baseline risks of cord blood sampling described above. Blood will be taken for rhesus and cord gas analysis as a priority, and we will only assess blood that is provided in surplus of these requirements. We will not use cord blood that is otherwise required for essential investigations at the time of birth. As such, research activities will not disrupt any standard care.

## 6.4. PARTICIPANT RECRUITMENT AND SCREENING

All patients giving birth at RPAH will be eligible for recruitment. Screening and recruitment will take place on admission to the birthing suite at the discretion of the midwife.

## 6.5 RECRUITMENT OF ABORINGINAL AND TORRES STRAIGHT ISLANDER PATIENTS

In line with the National Best Practice Guidelines for Collecting Indigenous Status in Health Data Sets (AIHW 2010) we will be collecting demographic data on identification of Aboriginal or Torres Strait Islander origin.

In accordance with the National Statement, Chapter 4.7, we will seek ethical approval from the HREC of the Aboriginal Health and Medical Research Council (AHMRC). Cultural differences and power differentials will be mitigated by being transparent in the consent process, engaging in open dialogue with participants and inviting cultural representatives/family members and social supports to guide the decision making process.

## 6.6. PARTICIPANT ENROLMENT

Participants will be enrolled into the study after the informed consent process has been completed and the participant has been assessed to meet all the inclusion criteria and none of the exclusion criteria. Study participants will receive a study enrolment number and this will be documented in the participant's medical (or personal) record and on all study documents.

## 6.7. INFORMATION AND CONSENT

Informed consent will be obtained from the eligible person giving birth on admission to the birthing suite or labour ward prior to their enrolment in the trial. The participant will be allowed time to discuss with family and a midwife prior to signing consent. The exportation of these biospecimens will be outlined in the Patient Information and Consent Form and all cryotubes sent internationally will be de-identified with barcodes.

A Patient Information Consent Form will be signed by the participant and a copy will be provided to the patient/person responsible as well a copy filed in their medical record. The original consent form will be stored with the study file in a secure locked location within Royal Prince Alfred Hospital. All paper source documents will only be accessible by midwives or research staff who require access.

## 6.8. RANDOMISATION PROCEDURE

No randomisation will take place as part of this study as per study design.

### Blinding

No blinding will take place as part of this study as per study design.

## 6.9. END OF STUDY TREATMENT/WITHDRAWAL PROCEDURE

The study will end once patient medical records have been assessed.

## 6.10. PATIENT WITHDRAWAL

Patients or persons responsible may withdraw through proxy consent or if their treating clinician believes it in their best interest to not continue.

## 7. OUTCOMES

### 7.1. DEFINITION OF OUTCOMES

'Healthy delivery' will denote a neonate that does not require an emergency caesarean section, prolonged resuscitation at birth, admission to the special care baby unit (SCBU) or neonatal intensive care unit, any re-admission to hospital in the 2 weeks following birth, or has any other documented adverse outcomes (including APGAR score of <7 at 5 minutes) or death in the perinatal period. Healthy deliveries will have no serious documented congenital abnormality, growth restriction or other developmental issue. Babies with no antenatal care data available will be assumed to be developmentally healthy unless there are documented perinatal adverse events.

An adverse outcome will be considered as the presence of any of the above. Intrapartum factors (e.g., abnormal foetal scalp blood sample lactate/pH and cardiotocography abnormalities) will also be considered an adverse outcome for the purpose of analyses.

APGAR scores from 1 and 5 minutes after birth will be collected from the medical record

Gestational weight will be obtained by the first recorded weight following birth

Gestational age will be recorded as per the medical record

Duration of the second stage of labour will be defined as the time from full cervical dilatation (as per progress notes) to the documented time of birth

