### 8.2. PROVIDE A DETAILED ANALYSIS PLAN

Differences in plasma NfL and tau between healthy neonates and those with adverse outcomes will be assessed by independent samples t tests or Mann–Whitney U tests, depending on distribution.

The area under the curve (AUC) of the receiver operating characteristic (ROC) curve will be calculated to assess the test characteristics of elevated cord blood NfL and tau in the prediction of adverse perinatal outcomes. Outcomes will be selected for ROC analysis if there is a statistically significant difference observed between healthy/diseased

neonates. The threshold elevation will be determined specifically for each outcome of interest, based on the observed difference in biomarker concentrations between groups. We will compare this to the AUC for CTG abnormalities (binary: present/absent) and scalp lactate elevation for the prediction of the same outcomes.

The normal range of plasma NfL and tau for healthy neonates will be established using the value range in which 95% of confirmed healthy neonates fall.

Scalp blood lactate concentrations will be compared to umbilical cord NfL and tau concentrations using linear regression. The correlation between the presence CTG abnormalities and NfL and tau concentrations will be assessed by independent samples t-test or Mann–Whitney U test, depending on distribution

Our initial analyses will be done independently for elective caesarean section deliveries vs. all other deliveries. However, further adjustments to baseline data may be required. Levels of tau and NfL for the above four analyses may be adjusted based on the multivariable regression analysis described below, if some factors (e.g., gestational age) are revealed to likely confound the outcome.

Linear regression models will be used to assess the correlation between gestational age, birth weight, and duration of 2nd stage of labour and plasma NfL/tau. The relationship between mode of delivery and plasma NfL/tau will be compared using independent samples t test or Mann–Whitney U test, depending on distribution. All the aforementioned variables will be combined into a multivariable regression model for the prediction of plasma NfL/tau to increase precision and adjust for confounders.

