### **Intrapartum factors**

Factor	Outcomes
Prelabour rupture of membranes	PROM PROM >24 hours from birth None Not applicable Unknown
Preterm Birth (<37 weeks)	Yes/No/Unknown
Induction of labour	Required Not required Unknown  Notes: (AROM, cervical ripening methods, etc.)

Duration of 1st stage of labour	4. _____ hours/not applicable
Duration of 2nd stage of labour	5. _____ hours/not applicable
Fetal presentation	Cephalic Breech Transverse Oblique Unstable Unknown Fundic/cord presentation
Fetal distress	Yes/No/Unknown  Notes:
Fetal lactate sample + result	Sampled/not sampled/unknown  _____ mmol/L
Cardiotocography abnormalities	Present (Description: _____) Absent Not applicable Unknown
Pain management	Epidural Nitrous oxide Pethidine Other (Description: _____) None Unknown
Anaesthetic complications	Yes/No/Unknown  6. Description: _____
Caesarean section delivery	Category 1 – Reason: Category 2 Category 3

	Category 4 Not applicable Unknown
Uterotonic agent administration	Oxytocin (units) _____ Ergometrine (mg) _____ Syntometrine (units, mg) _____ Misoprostol (mcg) _____ Carboprost (mcg) _____ Carbetocin _____
Post-partum haemorrhage	Yes/no/unknown (text description)
Umbilical cord gas	pH: Base excess: pCO 2 : PO 2 :
Blood loss	_____ mL
Complications	Uterine rupture Umbilical cord prolapse Chorioamnionitis Puerperal sepsis Other (Description: _____) None Unknown

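### CTG and scalp lactate findings count as adverse outcomes and are also the comparator tests for those outcomes, so their AUC comparison with NfL/tau is invalid as written

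*Protocol*

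**What the plan says.** Protocol section 7.1 describes a healthy delivery by what is absent. It "will denote a neonate that does not require an emergency caesarean section, prolonged resuscitation at birth", and the list goes on through unit admission, readmission and low 5-minute APGAR to a catch-all: "or has any other documented adverse outcomes". The next paragraph adds monitoring findings, abnormal scalp lactate/pH among them, to the adverse outcomes: "cardiotocography abnormalities) will also be considered an adverse outcome for the purpose of analyses".

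Section 8.2 plans ROC curves for the "test characteristics of elevated cord blood NfL and tau in the prediction of adverse perinatal outcomes". Outcomes enter that analysis through a contrast with the healthy group: "Outcomes will be selected for ROC analysis if there is a statistically significant difference observed between healthy/diseased" neonates. The comparison with current monitoring follows: "We will compare this to the AUC for CTG abnormalities (binary: present/absent) and scalp lactate elevation for the prediction of the same outcomes".

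Neither section sets CTG or lactate aside from the outcome, or from the healthy-group exclusions, when they serve as the test being judged. Section 3.2 lists adverse perinatal outcomes (objective 2) and intrapartum monitoring (objective 5) separately, but section 7.1 merges them.

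**The concern.** A test should not help to define the outcome it is judged against. Here CTG and scalp lactate do, and NfL and tau do not. The advantage goes to the existing monitoring, in the one analysis that sets the biomarkers directly against it. Section 1.2 gives the long-term hope as a biomarker that supplements or replaces scalp lactate testing, and describes this study as groundwork for a district-wide cohort. A biased comparison could make a useful marker look inferior to a CTG that carries little information, and that impression would go into the design of the next study.

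**Working it through.** **The plan's own figures.** The protocol states no AUC, outcome rate or CTG abnormality rate, so there is no figure on this point to reproduce. The sample size in section 8.1 rests on the precision of mean NfL and does not enter.

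**Assumed inputs.** Clinical outcome rate p = 15% (range 10 to 20%). CTG abnormality rate q = 25% (range 15 to 35%). CTG is unrelated to the clinical outcome, so its true AUC is 0.50. For a binary test, AUC = (sensitivity + specificity)/2.

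**1. Who is in the healthy group.** The catch-all in the healthy definition excludes any documented adverse outcome, and the next paragraph makes an abnormal CTG one. No healthy baby then has an abnormal CTG, so specificity = 1 whatever the CTG can detect.

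**2. Single clinical outcome against healthy controls.**
- Sensitivity of an uninformative CTG = q, so AUC = (q + 1)/2 = (0.25 + 1)/2 = 0.625.
- Range: (0.15 + 1)/2 = 0.575 to (0.35 + 1)/2 = 0.675.
- With an assumed CTG sensitivity of 0.60 and specificity of 0.70, the true AUC is (0.60 + 0.70)/2 = 0.65. Against healthy controls it becomes (0.60 + 1)/2 = 0.80.
- A marker with true AUC 0.75, unrelated to CTG given the outcome, stays at 0.75. It would then rank below this CTG instead of above it.

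**3. Composite outcome: clinical event or abnormal CTG.**
- Prevalence = 1 − (1 − 0.15)(1 − 0.25) = 0.3625.
- CTG sensitivity = 0.25/0.3625 = 0.69, and specificity = 1.
- AUC = (0.69 + 1)/2 ≈ 0.84.
- Lowest (p = 20%, q = 15%): prevalence 0.32, sensitivity 0.47, AUC 0.73. Highest (p = 10%, q = 35%): prevalence 0.415, sensitivity 0.84, AUC 0.92.
- The same marker is diluted by CTG-only cases. The share of cases with a clinical event is 0.15/0.3625 = 0.414, so its AUC = 0.414 × 0.75 + 0.586 × 0.50 ≈ 0.60.

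**4. Scalp lactate.** Take it as binary, with the same cut-off in both sections.
- Lactate uninformative and abnormal in only 30% of CTG-abnormal babies: abnormal rate 0.30 × 0.25 = 0.075, sensitivity against the composite 0.075/0.3625 = 0.207. AUC rises from 0.50 to 0.60.
- Lactate accurate (assumed sensitivity 0.80, specificity 0.90, true AUC 0.85) and independent of CTG given the outcome: abnormal rate 0.15 × 0.80 + 0.85 × 0.10 = 0.205. The three-part composite has prevalence 1 − 0.85 × 0.75 × 0.90 = 0.426. Sensitivity = 0.205/0.426 = 0.48, and AUC falls to (0.48 + 1)/2 = 0.74.

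**5. With the overlap removed.** If CTG is in neither the outcome nor the control exclusions, the uninformative CTG returns to 0.50.

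**The case against.** The strongest reply is that section 8.2 can be read as working outcome by outcome, with a threshold for each. A single clinical outcome compared with every birth that lacks it would show no inflation at all. That is true, but section 8.2 frames the contrast as healthy against diseased, and section 7.1 takes CTG-abnormal babies out of healthy. The partial bias in step 2 therefore follows from the text. What stands is that 0.84 is conditional: a reader might take it as the size of the problem, but the protocol never specifies a composite ROC.

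Three further inferences go beyond the documents.
- A reader might infer that the same baby falls in both comparison groups, because the healthy definition does not name CTG. The catch-all for other documented adverse outcomes, read with the next paragraph, removes such babies from healthy.
- A reader might infer that lactate's AUC must be inflated. Step 4 shows that it can fall against a composite. The comparison is still invalid, because lactate is part of its own reference standard.
- A reader might infer that the main result is compromised. The primary endpoint (section 4.4) is the confidence interval for mean NfL, and neither it nor the sample size uses this definition. The links to outcomes and monitoring are secondary and described as preliminary, and the AUC comparison appears only in section 8.2.

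**Conclusion.** The point holds for the AUC comparison in section 8.2. It arises from two stated rules that conflict, not from detail left to a later document. Against healthy controls the upward bias for CTG comes from the definition and does not depend on assumed rates; its size does. An uninformative CTG would show about 0.62 (0.58 to 0.68) for a single clinical outcome, and about 0.84 (0.73 to 0.92) if a composite that includes CTG is used, with NfL/tau diluted in the composite. For lactate the comparison is invalid, but the direction of the error depends on the assumptions. It should be fixed; it does not threaten the study's primary purpose.

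Emergency caesarean raises a related but less certain worry. Section 1.2 connects scalp lactate with decisions on when to deliver, so this outcome may be decided partly on the tests under comparison. The protocol does not say so outright, so a sensitivity analysis is the proportionate response.

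**What to change.** For the AUC comparison in section 8.2 only:
- Define cases by the adverse outcomes in section 7.1 other than CTG and scalp lactate/pH findings.
- Define non-cases as all other births, whatever their CTG or lactate result.
- Repeat the comparison with emergency caesarean left out of the outcome.
- Compare each test with NfL/tau on the same babies. The CRF records lactate as "Sampled/not sampled/unknown", so a lactate AUC from sampled babies should not be set beside a biomarker AUC from everyone.

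Keep the section 7.1 definition for the normal range. Deleting the intrapartum sentence altogether would let babies with abnormal CTG or lactate into that range. Report CTG and lactate against NfL/tau under objective 5.

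The cost is wording, plus precision in any composite. At the assumed rates, cases would fall from 36.25% to 15% of births: among the 68 laboured births of section 8.1, from about 25 (0.3625 × 68) to about 10 (0.15 × 68). The AUC confidence intervals would be wider. For a single clinical outcome no cases are lost.

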## 8. STATISTICAL CONSIDERATIONS

### 8.1. SAMPLE SIZE OR POWER CALCULATION

On the basis of preliminary data showing that umbilical cord blood NfL is significantly lower in placentae of women undergoing elective caesarean than women who underwent laboured delivery, we decided to analyse these two populations separately. Based on one study of NfL in cord blood, we anticipate the interquartile range (IQR) of umbilical vein NfL in non-elective caesarean deliveries to be 17pg/mL. We converted this to a standard deviation (SD) using the rule of thumb  $SD = IQR/1.35$ . To ensure that the 95% confidence interval (CI) of the estimate of the true mean does not exceed 3pg/mL, we calculated a required sample size of 68 patients. An additional 12 patients were added to account for issues with biospecimen collection and unforeseen emergencies that make collection unfeasible, for a total of 80 patients. For deliveries that were elective caesarean sections, based on another study that delineated caesarean sections from vaginal deliveries, we estimated the IQR to be 10pg/mL. This results in a sample of 24 participants required to establish a 95%CI of 3pg/mL for the true population mean. We increased this to 30 patients to account for issues with blood collection and storage. The total sample size including all modes of delivery is therefore 110. We will include consented patients in whom an adequate sample of cord blood is unable to be obtained in the 110 participants, in order to inform the feasibility and sample size calculation of a future study. However, given the NfL/tau concentrations will not be obtained, these patients will be omitted from the analysis.

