## Summary

Study title:	Benefits of Analysing Brain Biomarkers in perinatal care: a prospective observational cohort study ( BABBIES Trial )
Protocol version	V 1, dated 29/05/2022
Objectives	
Primary objective	1) Provide feasibility data on the testing of umbilical cord blood for NfL and tau
Secondary objectives	

1) Provide a “normal range of plasma NfL and tau” associated with normal healthy deliveries

2) Provide preliminary data linking cord blood NfL and tau to adverse perinatal outcomes

3) Compare cord blood NfL and tau in elective caesarean deliveries to other deliveries involving a period of labour

4) Provide preliminary data linking cord blood NfL and tau to foetal developmental abnormalities

5) Provide preliminary data linking cord blood NfL and tau to abnormalities on intrapartum monitoring (CTG, scalp lactate)

6) Assess the impact of gestational age on plasma NfL and tau

7) Assess the impact of birth weight on plasma NfL and tau

8) Assess the impact of the duration of the 2nd stage of labour on plasma NfL and tau

9) Determine the proportion of consented patients in whom inadequate cord blood is not collected

Study design	Prospective observational cohort study
Planned sample size	110
Selection criteria	Caesarean deliveries and deliveries involving a period of labour
Study procedure	Umbilical artery and vein cord blood samples (3mL) will be obtained from births at RPAH by the midwife (when feasible)
Statistical considerations	A sample size of 92 placentae (24 elective caesareans, 68 laboured deliveries) is required to ensure that the value for the mean plasma NfL has a 95% confidence interval not exceeding 3pg/mL, with an added 20% (18 patients) to account for issues with biospecimen collection and storage and non-healthy deliveries.
Duration of the Study	6 months

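### The required 68 and 24 samples are said to ensure a 95% CI for mean NfL within 3 pg/mL, but give only about even odds of it in each stratum

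*Protocol*

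**What the plan says.** Section 8.1 of the Protocol sizes two strata separately.

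- **Laboured (all deliveries other than elective caesarean).** The input is "we anticipate the interquartile range (IQR) of umbilical vein NfL in non-elective caesarean deliveries to be 17pg/mL". The conversion is described as "We converted this to a standard deviation (SD) using the rule of thumb" SD = IQR/1.35. The purpose is "To ensure that the 95% confidence interval (CI) of the estimate of the true mean does not exceed 3pg/mL", and the result is "we calculated a required sample size of 68 patients".
- **Elective caesarean.** Here "we estimated the IQR to be 10pg/mL", and "This results in a sample of 24 participants required to establish a 95%CI of 3pg/mL for the true population mean".

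Enrolment is raised to 80 and 30, or 110 in all, to allow for failed collection. Participants without an adequate sample count towards the 110 but are left out of the analysis.

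The Summary repeats that 92 placentae (24 + 68) "is required to ensure that the value for the mean plasma NfL has a 95% confidence interval not exceeding 3pg/mL". Section 4.4 makes the same quantity the primary endpoint: "95% confidence interval for mean umbilical cord plasma NfL of 3pg/mL or less". Section 2 states it as a hypothesis about the range of a single interval, below 3 pg/mL, across the 110 samples.

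The Protocol nowhere says half-width or margin of error, names no interval method for the mean, and gives no probability of reaching the target.

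**The concern.** A formula with a known SD fixes the width that would result if the sample SD equalled the planning value. It does not fix the width that will be observed. The sample SD falls above its planning value about as often as below it, so a size chosen to sit just under the target gives about a coin-toss chance of meeting it. The Protocol nevertheless describes 68 and 24 as ensuring the result.

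This matters because the primary endpoint is worded as a check on the observed interval against 3 pg/mL, and it is the Protocol's only numerical success criterion. Planning could be right in every respect and the hypothesis could still fail by chance. The Protocol also intends its results to inform the sample size of a later study, so the basis of the precision claim should be stated correctly.

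**Working it through.** **Inputs (section 8.1).** IQR 17 and 10 pg/mL; SD = IQR/1.35; 95% confidence; target 3 pg/mL; required n 68 and 24; enrolled n 80 and 30.

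**Step 1: planning SDs.** 17/1.35 = 12.593 and 10/1.35 = 7.407.

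**Step 2: reproduce the plan's numbers.** n = (1.96 × SD / w)².

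- With w = 3 as a half-width: 67.68, rounded up to 68, and 23.42, rounded up to 24. Both match.
- With 3 as a total width (w = 1.5): 271 and 94. Neither matches.

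So the plan's arithmetic is a half-width calculation with the SD known. The half-widths are 2.993 at 68 and 2.964 at 24.

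**Step 3: expected half-width with an estimated SD.** For a t interval this is t(0.975, n−1) × c₄(n) × SD / √n, where c₄ is the ratio of the mean of the sample SD to the true SD under normality.

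- n = 68: 1.9960 × 0.99628 × 12.593 / √68 = 3.037 (3.048 if the sample SD equals the planning SD).
- n = 24: 2.0687 × 0.98919 × 7.407 / √24 = 3.094 (3.128 likewise).

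With a z interval the expected half-widths are 2.98 and 2.93.

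**Step 4: probability that the observed half-width is 3 or less.** P = Pr{χ²(n−1) ≤ n(n−1)[3/(k × SD)]²}, with k = t(0.975, n−1) or 1.96. At n = 68 with t, the bound is 64.90 on 67 degrees of freedom, so P = 0.450. At n = 24 with t, it is 21.16 on 23 degrees of freedom, so P = 0.429.

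| | Laboured | Elective |
|---|---|---|
| 68 / 24, t interval | 45.0% | 42.9% |
| 68 / 24, z interval | 53.4% | 57.2% |
| 70 / 26, t interval | 51.9% | 54.5% |
| 80 / 30, no losses, t interval | 82.4% | 76.5% |

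A simulation of 100,000 runs at 68 and 24 with t intervals gave 45.2% and 42.7%.

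**Step 5: size for an expected t half-width of 3 or less.** The smallest n are 70 (expected 2.992) and 26 (expected 2.962). The total is 96, which leaves 110 − 96 = 14 for losses, against 110 − 92 = 18 now. If the half-width is instead evaluated at the planning SD, 70 gives 3.003, so 71 is needed; 26 gives 2.992 and stands.

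**Step 6: a pooled mean, for comparison.** One interval on 68 + 24 = 92 samples, with the planning SDs, has a t half-width of about 2.4 if the strata share a mean, and about 2.5 if their means differ by an assumed 10 pg/mL. In simulation it was 3 or less more than 99% of the time in both cases. The total width, about 4.8 with equal means, would not meet 3.

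**The case against.** Several points on the other side stand.

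- **The formula is conventional and was applied correctly.** The expected excess over 3 is about 1% and 3%, and two more analysable samples per stratum remove it. The borrowed IQRs are a larger source of uncertainty. But a sound approximation for an expected width still does not support a claim to ensure the observed one.
- **The Protocol does not specify a t interval for the mean.** It mentions t tests only for group comparisons. With a z interval the expected half-widths fall below 3. The chances of passing are then 53% and 57%, so the guarantee fails on either method.
- **Enrolment is 80 and 30.** If every sample were analysable, the chances would rise to 82.4% and 76.5%. The increase is meant to absorb losses, however, and the guarantee is attached to 68 and 24.
- **The criterion may be meant for one pooled mean.** Sections 2 and 4.4 can be read that way. On a pooled half-width reading the target would almost certainly be met at 92. Section 8.1 does not size the study on that basis.

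A reader might multiply the two stratum probabilities and conclude that the study has only about a 19% chance of success (0.450 × 0.429 = 0.193). That needs a rule that both strata must pass, and the Protocol contains none. Nor does it attach any action to missing 3 pg/mL; the stated primary objective is feasibility data.

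**Conclusion.** The point holds as a correction to what the Protocol claims for its sample size. At 68 and 24 the target is not ensured: the chance is 45% and 43% with a t interval, or 53% and 57% with a z interval. These figures assume normal data, true SDs equal to the planning SDs, exactly 68 and 24 analysable samples, and 3 pg/mL read as a per-stratum half-width. Skewed data would lower them: an assumed lognormal with median 23.3 and IQR 17 gives about 13% at 68 with a t interval.

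The documents do not show that the sample-size arithmetic is wrong, that the study is likely to fail overall, or that 110 is too few for a per-stratum expected half-width of 3. The half-width reading is itself inferred from the arithmetic. The hypothesis speaks of the range of the interval, which reads as a total width and would need 271 and 94 even on the plan's own formula. That ambiguity is the larger issue and has to be settled first.

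**What to change.** Keep 110 participants and proceed in this order.

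1. In the Summary, section 2, section 4.4 and section 8.1, state in the same terms whether 3 pg/mL is a half-width or a total width, and whether it applies to each stratum or to a pooled mean. Changing only the Summary and 8.1 would leave them in conflict with the hypothesis and the endpoint.
2. If a per-stratum half-width is meant, replace the claim to ensure the target with a statement that the sizes give an expected half-width of about 3 pg/mL.
3. Name the t interval and restate the required numbers as 70 and 26 (96, allowance 14), or as 71 and 26 (97, allowance 13) if the half-width is evaluated at the planning SD. Say which definition is used.
4. State the probability of meeting the criterion: about 52% and 55% at 70 and 26, and 82.4% and 76.5% at 80 and 30 with no losses.
5. Report the observed interval as the result, and do not treat a narrow miss as failed feasibility.

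On the per-stratum half-width reading the cost is wording only. The stated precision becomes slightly less favourable and the allowance for losses falls from 18 to 14 (or 13). If a total width is meant, these replacement figures do not apply and the sizing has to be redone.
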